9.34 Individual Subject Dose Evaluation and Adjustments

Doses of ETR will be adjusted in an individual subject to attain an AUC_{12h} of $< 2350 \text{ ng}\cdot\text{h}/\text{mL}$.

- If the subject's current dose is well tolerated (no toxicity \geq Grade 3) but AUC_{12h} is $< 2350 \text{ ng}\cdot\text{h}/\text{mL}$, then a new dose will be determined by prorating the current dose to attain an AUC_{12h} of approximately $2864 \text{ ng}\cdot\text{h}/\text{mL}$ (the 20th percentile of exposure in adults). The maximum dose increase for the initial PK-guided dose adjustment would be capped at the adult dose of 200 mg twice daily. If a second PK evaluation again reveals an $AUC_{12h} < 2350 \text{ ng}\cdot\text{h}/\text{mL}$, then the dose may be increased above the 200 mg twice daily initial BID cap, again, targeting an AUC_{12h} of approximately $2864 \text{ ng}\cdot\text{h}/\text{mL}$.
- If the subject's AUC_{12h} is $> 4380 \text{ ng}\cdot\text{h}/\text{mL}$ (the median AUC_{12h} value in adults receiving ETR 200 mg twice daily) but current dose is not well tolerated (no toxicity \geq Grade 3) then the dose will be prorated, if possible given available dosage forms to achieve an AUC_{12h} of $4380 \text{ ng}\cdot\text{h}/\text{mL}$. If no dose reduction is possible, then the subject will be discontinued from study treatment.
- If a subject has not achieved an AUC_{12h} of $< 2350 \text{ ng}\cdot\text{h}/\text{mL}$, but is experiencing a Grade 3 or greater toxicity that is deemed probably or definitely related to study drug, that subject will be discontinued from study treatment.

Although ETR displays non-proportional PK, dose adjustments will be prorated on a linear scale using multiples of 12.5 mg (the smallest incremental dose change possible given the available formulations).

Initial PK-guided dose increases will be capped at the adult dose of 200 mg twice daily. However, if after a second PK evaluation the subject's AUC_{12h} has not achieved the minimum target (2350 ng•h/mL), doses may exceed 200 mg twice daily. The core protocol team will communicate all individual dose adjustments to the participating site.

All subjects with an individual dose adjustment (not related to weight gain) will have repeat intensive 12 hour PK evaluations performed between Day 7 to 14 after initiation of the new dose.

Subjects who require a dose adjustment but refuse to undergo repeat intensive PK (see Section 9.34 for management of individual dose adjustments) will have ETR therapy discontinued and will be replaced.

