6.0 SUBJECT MANAGEMENT

6.1 Toxicity Management

The DAIDS Table for Grading the Severity of Adult and Pediatric Adverse Events, (DAIDS AE Grading Table), Version 1.0, December 2004, Clarification August 2009, must be used and is available on the RSC website at (<http://rsc.tech-res.com/safetyandpharmacovigilance/>).

Management of adverse experiences will be according to the best clinical practice and the judgment of the site investigator. Alternate explanations for clinical and laboratory abnormalities must be sought.

Laboratory normal ranges will be the institutional values. However, if a site does not have an age-specific normal range/value for a particular laboratory, the site should use the latest edition of the Harriet Lane Handbook for normal ranges/values and document this for monitoring purposes. Abnormal clinical and laboratory findings should be followed until resolution to < Grade 2.

The toxicity management guidelines are for events for which a relationship to study drugs cannot be excluded. Clinical or laboratory adverse events (AEs) that are definitely unrelated to study drug(s) may not

result in study drug interruption. General guidelines for study drug suspected adverse drug reactions (SADRs) are provided below:

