6.12 General Management Guidelines

NOTES:

- All antiretroviral therapy including study drug should be started or stopped together whenever possible, except for when one antiretroviral agent can be substituted for another within the same class, when the etiology of the toxicity can be determined.
- If a subject is pending a safety event analyses or resolution, additional safety tests may be required by the team.

Grade 1

Continue study drug; routine monitoring.

Grade 2

Continue study drug; monitor closely with more frequent visits; as per site investigator, work-up to exclude other causes.

Grade 3

NOTE: Grade 3 triglycerides and cholesterol events will NOT require the subject to stop study drug or OBR.

- The protocol team should be notified of a Grade 3 event at [contact].
- Study drugs can be continued at the discretion of the site investigator/clinician while awaiting a repeat assessment/confirmation of an abnormal laboratory test as soon as possible (within 72 hours).
- If the repeat assessment confirms Grade 3 toxicity, AND if the investigator considers the event to be at least possibly related to study drug, ETR should be withheld and any abnormal laboratory values should be followed weekly (Except in Grade 3 cholesterol and triglycerides).

- OBR should be held at the discretion of the site investigator.
- If the toxicity resolves to \leq Grade 2 within 21 days, ETR (and OBR if applicable) can be restarted.
- If the Grade 3 toxicity persists for $>$ 21 days, or recurs at a \geq Grade 3 after re-introduction of ETR; ETR must be permanently discontinued.

Grade 4: Non-Life-Threatening Toxicity

- Study drug (ETR) and concomitant antiretrovirals (OBR) should be discontinued immediately unless the clinician and P1090 core protocol team, believe that withholding OBR and/or ETR would be harmful to the subject and that continuing the drugs would pose little additional risk.
- Sites should attempt to confirm any unexpected laboratory results as soon as possible, but always within 72 hours of the event to determine if these results were spurious.
- The protocol team should be notified of a Grade 4 event at [contact].
- If the repeat assessment confirms Grade 4 toxicity, ETR should be permanently discontinued, HOWEVER, for Grade 4 adverse events that are determined to be unrelated to study drug, the investigator should contact the team to determine when study drug may be safely resumed.

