6.16 Management of Neurologic Adverse Events

NOTE: Please refer to Appendix VI for grading abnormal neurologic adverse events. Grade 1

Continue study drug; routine monitoring.

Grade 2

Continue study drug; work-up to exclude other causes according to judgment of site investigator. Grade 3

- Subjects experiencing a Grade 3toxicity must have ETR discontinued
- OBR may be discontinued at the discretion of the site investigator.
- The protocol team should be notified of a Grade 3 event at [contact].
- For Grade 3 adverse events that are determined to be unrelated to study drug, the investigator should contact the team to determine if/when the study drug may be safely resumed
- If the event is considered to be ‘definitely related,’ ‘probably related’ or ‘possibly related’
- to study drug, AND is resolved to grade 2 or less, AND the site physician feels it is in the subjects best interest to re-try the drug, the investigator should contact the team to determine if/when the study drug may be safely resumed
- If subjects are permanently discontinued from ETR, they will still be followed on study on a modified schedule (Appendix IE) for safety outcomes. Subjects will be treated as clinically appropriate per the local physician.

Grade 4: Non-Life-Threatening Toxicity

- Subjects experiencing a Grade 4 adverse event must have ETR discontinued temporarily
- OBR should be held at the discretion of the site investigator.
- The protocol team should be notified of a Grade 4 event at [contact].
- For Grade 4 adverse events that are determined to be unrelated to study drug, the investigator should contact the team to determine when/if study drug may be safely resumed.
- If the event is considered to be definitely related, probably related or possibly related to study drug, ETR should be permanently discontinued.
- If subjects are discontinued from ETR, they will still be followed on study on a modified schedule (Appendix ID) for safety outcomes. Subjects will be treated as clinically appropriate per the local physician.

Grade 4: Life-Threatening Toxicity

- Subjects experiencing a Grade 4 toxicity must have ETR discontinued permanently; but should remain on study for safety follow-up.
- OBR should be held at the discretion of the site investigator.
- The protocol team should be notified of a Grade 4 event at [contact].

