6.8 Criteria for Etravirine (Study Drug) Discontinuation

The following are criteria that will result in discontinuation of study treatment (ETR). Subjects who are withdrawn from study drug within the first 48 weeks of study will not enter long term follow-up, but will be followed for safety for 4 weeks, as per Appendix ID.

Additionally, any AEs will be followed until satisfactory clinical resolution (i.e. value returns back to subjects baseline value) or stabilization (to be agreed upon with the sponsor). All Grade 3 and Grade 4 laboratory abnormalities as well as any laboratory abnormalities resulting in an increase of 2 DAIDS grades from baseline will be followed until they return to baseline or within 1 grade from baseline.

- Grade 3 or higher events that are believed to be related, or possibly related, to study drug
- Treatment with disallowed medications
- Grade 3 or higher cutaneous reactions as outlined in section 6.13, that are not clearly related to a specific viral illness
- Grade 3 or higher acute systemic allergic reactions as outlined in section 6.14, that are related to study drug
- Other Grade 3 or higher toxicities that don't resolve to < Grade 3
- Grade 3 or higher ECG toxicities (QTc and/or PR interval) as outlined in Section 6.15, that are deemed related to study drug
- Grade 3 or higher neurologic adverse events as outlined in Section 6.16
- For subjects who have an $AUC > 4380\text{ng.h/mL}$, but who cannot be dose reduced
- Non-adherence to study medication or study medication administration instructions
- New data become available that indicate treatment should be discontinued
- Subject declines further study visits, including PK visits

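### Protocol 6.8 ends ETR for related Grade 3 events that 6.12 and 6.16 allow to be restarted, 9.34 prints its dose-reduction condition reversed, and no section is said to prevail

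*Protocol*

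**What the plan says.** Section 6.1 of the protocol sets the scope: "The toxicity management guidelines are for events for which a relationship to study drugs cannot be excluded". Section 6.12 and the general bullet of 6.8 therefore cover the same events.

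- **6.8, first bullet.** ETR is discontinued for "Grade 3 or higher events that are believed to be related, or possibly related, to study drug". The bullet has no exception for recovery or for lipids.
- **6.12, Grade 3.** If the repeat assessment confirms the grade, "AND if the investigator considers the event to be at least possibly related to study drug, ETR should be withheld". If the event resolves to Grade 2 or lower within 21 days, "ETR (and OBR if applicable) can be restarted". ETR stops permanently only if the event lasts longer or recurs. A note adds that "Grade 3 triglycerides and cholesterol events will NOT require the subject to stop study drug or OBR".
- **6.16, Grade 3 neurologic.** ETR is stopped. If a related event has resolved to Grade 2 or lower "AND the site physician feels it is in the subjects best interest to re-try the drug", the team decides whether and when to resume.
- **9.34, second bullet.** For AUC12h above 4380 ng·h/mL the dose is reduced under the condition "but current dose is not well tolerated (no toxicity", completed by Grade 3 or more. If no reduction is possible, ETR stops.
- **6.8, AUC bullet.** ETR stops for children above 4380 "but who cannot be dose reduced". Tolerability is not mentioned.

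**The concern.** A child with a reversible, possibly related Grade 3 event can be withdrawn under 6.8 or held and restarted under 6.12. Both are written as instructions, and neither defers to the other.

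The choice feeds several counts:

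- the primary toxicity endpoint of termination due to a suspected adverse drug reaction (Protocol 8.21);
- the table of discontinuation reasons (SAP 6.1);
- the rule in Protocol 3.3 that children stopped for ETR toxicity are counted as failures and not replaced;
- the Grade 3 part of the cohort safety rules in 8.512 and 8.513, when the event falls by Week 4.

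The 9.34 bracket and the 6.8 AUC bullet raise a similar doubt about who is dose-reduced or stopped for high exposure.

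**Working it through.** **Step 1: the sections side by side.**

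| Situation | 6.8 | Specific section |
|---|---|---|
| Confirmed, at least possibly related Grade 3 event | Discontinue | 6.12: hold; restart if Grade 2 or lower within 21 days |
| Related Grade 3 cholesterol or triglycerides | Discontinue | 6.12: no stop required |
| Related Grade 3 neurologic event | Discontinue under the general bullet (the neurologic bullet itself points to 6.16) | 6.16: re-trial possible |
| Low AUC with Grade 3+ toxicity | Discontinue if possibly related | 9.34, third bullet: discontinue if probably or definitely related |
| AUC12h > 4380, no reduction possible | Discontinue | 9.34, second bullet: only under a tolerability condition |

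The stricter attribution threshold in the fourth row does no work if 6.8 already stops every possibly related event. The rash and allergic rules require a stop at Grade 3 in their own sections, and the ECG rule stops ETR for a confirmed, related Grade 3 finding. These three do not conflict with 6.8.

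**Step 2: does 6.8 mean a temporary hold?** Its opening text says that children withdrawn from drug in the first 48 weeks get four weeks of safety follow-up and do not enter long-term follow-up. That describes permanent withdrawal.

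**Step 3: the 9.34 bracket.** The first bullet explains a well-tolerated dose as one without toxicity of Grade 3 or more. The second bullet negates the term but keeps the explanation. As printed, it reduces the dose of a child who has no Grade 3 toxicity.

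**Step 4: the 6.8 AUC bullet.** Section 9.34 gives 4380 as the adult median. The acceptable range for a cohort geometric mean in 9.31 is 2713 to 6783, and 4380 lies inside it. Without a tolerability condition, a literal reading stops children with on-target exposure who cannot be dose-reduced.

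**Step 5: timing of lipids.** Cholesterol and triglycerides are scheduled at Entry and Weeks 12, 24 and 48 (Appendices IA to IC). The data for 8.512 and 8.513 end at Week 4, or earlier if the dose is adjusted. No scheduled on-drug lipid result falls in that window.

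**Step 6: effect on the cohort rule.** Let p be the rate of related Grade 3 events that end in termination and q the rate of life-threatening or attributable Grade 4 events. Then

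P(fail) = 1 − Σ(k=0..m) C(n,k) p^k (1−p−q)^(n−k),

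with m = 2 for n = 6 (8.512) and m = 3 for n = 12 (8.513, more than 25%).

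This reproduces all 11 rows of Table 8. For p = 0.25, q = 0 it gives 0.169 against the printed 0.17. For p = 0.05, q = 0 it gives 0.0022 against 0.002. The largest gap is 0.656 against 0.67.

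Now set q = 0. Suppose all related Grade 3 events end in termination (6.8), or half do (6.12 with some restarts). The half share is an assumption, because the documents give none. For n = 6 at a 10% rate:

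- all: 1 − (0.5314 + 0.3543 + 0.0984) = 0.016
- half (p = 0.05): 1 − (0.7351 + 0.2321 + 0.0305) = 0.002

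| Related Grade 3 rate | n = 6, all / half | n = 12, all / half |
|---|---|---|
| 10% (assumed) | 0.016 / 0.002 | 0.026 / 0.002 |
| 14% (see below) | 0.039 / 0.006 | 0.075 / 0.008 |

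The 14% row is the PIANO rate of Grade 3 or 4 AEs, (6 + 8)/101. It is all-cause, covers 48 weeks and comes from ages 6 to 17, so it is high for a related Grade 3 rate by Week 4.

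**Step 7: effect on the termination proportion.** Each reclassified child moves the aggregate by 1/36 = 2.8 points and a cohort of 12 by 1/12 = 8.3 points. With no other terminations, the exact intervals printed in Table 7 apply: 0/12 is 0% to 26%, and 1/12 is 0.2% to 38%.

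**The case against.** The strongest reply is that the protocol team would settle each case.

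- Grade 3 and 4 suspected reactions reach the team within 24 hours (6.11).
- The team answers toxicity questions within one business day and recommends all dose modifications (6.2).
- Safety data are reviewed at least twice a month during dose finding (8.5).
- For the start, stop and pause rules, attribution of serious events is by consensus, with the monitoring committee deciding disputes (8.511).

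This stands as a limit on divergence between sites. It does not say which section governs.

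Section 6 also uses discontinuation for temporary interruptions in places, and 6.8 has a separate bullet for other Grade 3 toxicities that do not resolve, which resembles 6.12. Both points soften the conflict. The unqualified first bullet still covers every related Grade 3 event, and the follow-up text in 6.8 still describes withdrawal.

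On 9.34, the intent can be recovered from the first bullet, and the core team communicates every individual adjustment. That stands: it is a wording reversal in a rule whose meaning can be inferred.

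A reader might infer three stronger things:

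- **That the lipid conflict can sway dose selection.** The visit schedule does not support this (Step 5). It can affect only later termination counts. The protocol also does not say that the two PIANO hypertriglyceridemia cases were related to ETR.
- **That the cohort rule is badly distorted.** At 25%, the n = 6 figures would be 0.169 and 0.029. Table 8 uses 25% and 50% only as hypothetical rates, and nothing in the documents anchors a related Grade 3 rate that high.
- **That children have been handled wrongly.** By 12 February 2016, 14 children were enrolled and AEs were reported as mainly unrelated to study product (Additional Safety Data, Section 1.3). No such case is shown.

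**Conclusion.** The inconsistency is real, and its severity is minor to should-fix. Section 6.8 contradicts 6.12 for reversible related Grade 3 events and for Grade 3 lipids, and its general bullet contradicts the re-trial in 6.16. The 9.34 bracket is printed reversed, and the 6.8 AUC bullet lacks the tolerability condition. No order of precedence is stated.

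The consequence is an ambiguous count of terminations in a primary endpoint, where one child in a cohort of 12 is 8.3 points. The effect on the Week 4 cohort rule is small at plausible rates. That conclusion rests on an assumed rate, an assumed half share and no life-threatening events.

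Table 8 is correct for the discontinuation rate it defines. The worst-grade summaries and Grade 3+ proportions in SAP 6.2 do not depend on whether ETR was stopped. The part of the cohort rule for life-threatening events, attributable Grade 4 events and death is also untouched.

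**What to change.** Issue a clarification memo or letter of amendment with three changes.

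1. **6.8, first bullet:** *Grade 3 or higher events at least possibly related to study drug, where Sections 6.12 to 6.16 or 9.34 require permanent discontinuation (Grade 3 cholesterol and triglycerides exempt, per 6.12).*
2. **6.8, AUC bullet:** add *and whose current dose is not well tolerated*.
3. **9.34, second bullet:** change the bracket to *(toxicity ≥ Grade 3, other than Grade 3 cholesterol or triglycerides)*, and say that any reduced dose applies when ETR is restarted under 6.12. Without the lipid exception, the corrected bracket would itself let a Grade 3 lipid result trigger a reduction or stop that 6.12 does not require.

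No new data or visits are needed, and 8.512, 8.513 and Table 8 stay as they are. The team should record which rule was applied to any related Grade 3 event so far.

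The downside is that fewer reversible events count as terminations than under a literal 6.8, so the Grade 3 part of the cohort rule trips less often (0.016 to 0.002 for n = 6 in the 10% example). If the team prefers the stricter 6.8 for infants, it should amend 6.12 and 6.16 instead. Either choice works if it is stated.

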9.35 Cohort Dose Evaluation and Adjustment

Enrollment will be temporarily halted after PK data are obtained for 6 subjects within a given mini cohort. PK parameters and 28-day safety data will be reviewed for these subjects. If safety data are acceptable, and the geometric mean AUC_{12h} of the first six is judged acceptable, then an additional 6 subjects will be enrolled to equal $N = 12$ in each full cohort. Failure with respect to the safety and/or PK guidelines will result in a dose adjustment within this cohort, with the starting dose adjusted in the appropriate direction.

NOTE: Please refer to Sections 6.6 and 6.8 if non-adherence is suspected.

Subjects who require a dose adjustment but refuse to undergo repeat intensive PK (see Section 9.34 for management of individual dose adjustments) will have ETR therapy discontinued and will be replaced (will remain on study but off study drug).

PK parameters for ETR will be summarized and descriptive statistics calculated. As stated, the AUC_{12h} for ETR is the primary PK parameter.

9.351 The dose of ETR will be judged acceptable if:

- The ETR dose is tolerated
- AND
- The geometric mean ETR AUC_{12h} is between 60% and 150% of the geometric mean AUC_{12h} in HIV-1-infected treatment-experienced adults from the DUET studies (i.e. between 2713 and 6783 ng•h/mL)

If a revised starting dose of ETR is needed, modeling and simulation will be used (incorporating all available PK data at that time) to propose a revised weight-based dosing table for ETR for which the calculated chance of success for a given age cohort (i.e., geometric mean AUC_{12h} between 60 and 150% of adults) will be at least 80% (see also Appendix III).

In making any revision to the starting dose, the team will estimate the C_{12h} expected with the revised dose. The goal of dose finding is to identify a dose that approximates ETR exposure in adults who receive an ETR dose of 200 mg twice daily (when given with darunavir/ritonavir). The median AUC_{12h} in adults is 4380 ng•h/mL and 75th percentile is 6339 ng•h/mL. The median C_{12h} in adults is 298 ng/ml and the 75% percentile is 467 ng/ml. The team will compare the expected C_{12h} with that achieved in adults, and may use this comparison to refine the revised starting dose to approximate both the AUC_{12h} and C_{12h} exposure.

Any change in the starting dose will be communicated by the protocol team to all participating sites via written notification.

As detailed in Section 3.0 of the protocol, subjects may be dose-adjusted to the new dose and additional new subjects will be treated at the new dose, and safety and PK will be evaluated as described.

If more than 2 of the 6 children in a cohort has an AUC_{12h} greater than the 75th percentile of adult values (6339 ng•h/mL) and the cohort has passed the safety criteria, the team will review the starting dose and the expected distribution of ETR C_{12h} and AUC_{12h} . This review is to assess the goal of objective of achieving a distribution for ETR C_{12h} and AUC_{12h} values in children that approximates that in HIV-1-infected treatment experienced adults. The team may decide to revise the starting dose; however, there is no requirement for the team to adjust the starting ETR dose.

If the starting dose for a cohort of older subjects is revised, the protocol team may preemptively change the starting dose for subsequent younger cohort that has not yet opened to enrollment. Any change in the starting dose will be communicated by the protocol team to all participating sites, with instructions to use the appropriate table of starting doses. It is not unreasonable to suspect that the three cohorts planned for enrollment may each have different dosage requirements. This protocol will determine appropriate doses for each of these strata.

